15. STUDY MONITORING PLAN	
16. DATA MANAGEMENT	
16.1. DATA COLLECTION	
16.2. DATA STORAGE	
16.3. Confidentiality	
16.4. Study Record Retention	
17. USE OF DATA, PUBLICATIONS POLICY, REGISTRATION	
18. BIBLIOGRAPHY	

PROTOCOL SYNOPSIS

Protocol Title:	EVALUATION OF APPLAUD MEDICAL'S ACOUSTIC ENHANCER WITH LASER LITHOTRIPSY SYSTEM IN THE TREATMENT OF URINARY STONES			
	Short Title: Acoustic Enhancer Research on Laser Lithotripsy (AEROLITH) Clinical Study			
Protocol Number: CIP-0001, Rev. E				
Study Objective:	A pivotal study to evaluate the safety and effectiveness of Applaud Acoustic Enhancer when used in conjunction with conventional ureteroscopic laser lithotripsy (URS-LL) in the treatment of subjects with urinary stones			
Study Design:	Prospective, multi-center, two-arm, randomized, double blinded study			
Device Name:	Applaud Acoustic Enhancer			
Intended Use:	The Applaud Acoustic Enhancer is indicated for use in ureteroscopic laser lithotripsy for the fragmentation of calcium-based urinary stones. When the Acoustic Enhancer is used in a laser lithotripsy procedure, Acoustic Enhancer microparticles generate additional stone-fragmenting shockwaves.			
Device Description:	Applaud's Acoustic Enhancer is provided in a lyophilized form. After reconstitution, it is a liquid, containing micron-scale particles that are made of a perfluoroalkane gas core with a lipid shell. The device is intended to be used with cleared/approved pulsed laser systems in fragmenting urinary stones (calculi) in the upper (superior) pole, lower (inferior) pole, and interpolar region of the kidney, pelvis of the kidney, and proximal ureter.			
Study Groups	Investigational Arm: Acoustic Enhancer with URS-LL Control Arm: URS-LL			
Sample Size and	196 randomized subjects will be enrolled in this study at up to 18 investigational sites			
Number of Sites:	located in the U.S. Each site may enroll no more than 20% of the total sample size of 196 subjects.			
Study Duration:	 The anticipated timeline for this study is as follows: Subject Enrollment: 12 months Follow up Visits: 14 Day telephone call follow up for adverse event monitoring 30 Day on site follow up visit 90 Day on site follow up visit for subjects who have unresolved hydronephrosis at the 30-Day visit 			
Patient Population:	Male or female subjects 18 to 75 years of age with a diagnosis of urinary stone disease			

Inclusion / Exclusion	Incl	usion Criteria:
Criteria	1.	Male or female aged \geq 18 years to \leq 75 years
	2.	Provides written informed consent
	3.	Patients with at least one urinary stone measuring 6mm or greater (but no more than a cumulative diameter of 20mm) located proximally to the iliac vessels on one side may be treated.
		Note 1: Punctate stones measuring $\leq 2mm$ do not count in in the cumulative diameter limit.
		Note 2: Some corroborating imaging may be required to exclude a patient if the investigator suspects that the stone has moved to middle/distal ureter (e.g. change in symptoms, an increase in serum creatinine).
	4.	Urinary stone(s) should be apparent on a CT scan within 60days prior to study enrollment. Stone assessment will be conducted using CT imaging following CLIN- 0025: AEROLITH IDE Study Screening Guide.
		Note 1: Soft tissue window will be used for stone measurement. Window width/level
		adjustments will be applied as necessary by the reviewer to improve stone evaluation. A bone window may help distinguish stones from ureteral stents. The region of interest will be magnified (approximately 400%) by the reviewer to clearly visualize the stone outline.
		For details, please refer to CLIN-0003.
		Note 2: If CT imaging has not been conducted yet for the patient, please follow CT image acquisition parameters detailed in CLIN-0002: Image Acquisition Protocol, AEROLITH Study
	5.	Patients with bilateral stones are allowed but only one side may be treated. Only the treated side will be evaluated for safety and effectiveness.
	6.	Patients may enter the study with a stent in place.
	7.	Patients presenting with absence of a Urinary Tract Infection as confirmed using urinalysis
		e: If the urinalysis is more than 7 days removed on the day of the procedure, a
		alysis and confirmation that the patient is free of UTI symptoms should be performed
	ont	he day of the procedure for the patient to be eligible to participate in the study.

Page 6 of 53

	Patients with stones exceeding a cumulative diameter of 20mm on the side to be
	treated. Note: Punctate stones measuring $\leq 2mm$ do not count in the side to be
	diameter limit.
2.	Patients with ureteral stones located distal to the iliac vessels on the side to be
2.	treated
3.	
5.	Imaging
4.	For patients who have a ureteral stent in place, patient is excluded if stent is
	calcified or encrusted as verified using standard of care imaging (e.g., KUB X-ray)
5.	Patients who have had prior URS-LL within 3 months on the side to be treated at
	the time of consent
6.	History of cystinuria
	Urine pH is < 5.5. Note: If a patient's largest stone measures a mean stone intensity
	of \geq 500HU and the patient has a historical pH value of \geq 5.5, a recently tested
	(within 30 days of consent) urine pH showing <5.5 in this case does not exclude a
	subject.
8.	Patients with known history of recurrent uric acid stones
	Untreated urinary tract infection (UTI)
	History of drug resistant chronic UTI
	If female, pregnant as confirmed using urine or serum test to be conducted on the
	day of the procedure
12.	Patient has an American Society of Anesthesiologists (ASA) physical classification
	level of 4 or greater.
13.	Known sensitivity to possible medications used before, during, or after the URS
	Laser Lithotripsy procedure, including but not limited to the following: sedative
	agents, general anesthetics, topical anesthetics, and opioid analgesics
14.	Stones suspected in calyceal diverticula
15.	Horseshoe kidney
16.	Congenitally ectopic pelvic kidneys
17.	Full staghorn calculi >2cm
18.	Patients with elevated serum creatinine > 1.5mg/dl
	Patients with a solitary kidney
20.	Malrotated kidney on the side with urinary stone
21.	Duplicated collecting system or duplicated ureters
22.	Patients who are currently involved in any investigational drug or device trial or
	have been enrolled in such trials within 30 days of index procedure
23.	Patients who are actively taking antiplatelet and anti-coagulation except low dose
	aspirin
	Prostate biopsy within the last 3 months
	History of radiation therapy of abdomen and pelvis
26.	History of urinary tract reconstruction

	27. Other factors that the investigator feels would interfere with the participation and
	completion of the study such as:
	 Inability to provide voluntary consent
	 Inability to understand the clinical investigation or cooperate with
	investigational procedures
	 Planned relocation or unable to return for required follow-up visits
	• Vulnerable individuals (mentally disabled, physically disabled, prisoner,
	etc.)
Primary Safety	The rate of occurrence of each arm of clinically significant serious adverse events
Endpoint:	defined as:
Enupoint.	
	Serious infection (urosepsis, pyelonephritis) requiring hospitalization and
	treatment through 90 days post index procedure
	 New urinary tract stricture formation requiring surgical intervention through 90 days past index precedure
	days post index procedure
	Confidence intervals will be presented to aid in the evaluation of the incidence of
	clinically significant serious adverse events, both for each treatment group individually,
	and for the difference in the rates between the two treatment groups.
Primary Efficacy	Treatment success is defined as the proportion of study subjects who have a complete
Endpoint:	absence of stones or have residual fragments measuring ≤ 2 mm on the treatment side,
	as assessed by CT imaging through 30-day follow-up post index procedure.
	The primary efficacy endpoint will demonstrate that the investigational arm (Acoustic
	Enhancer with URS-LL) is superior in the fragmentation of stones to ≤ 2mm versus the
	control arm (URS-LL).
Secondary Efficacy	Total radiant energy (TRE): Mean value of laser energy, measured for each subject in
Endpoint:	kilojoules divided by the stone cross-sectional area. The secondary endpoint will
	demonstrate non-inferiority of the mean TRE used between the investigational arm and
	the control arm.
Additional	Mean total lasering time
Observations:	 Additional interventional stone procedures for stone(s) that were treated as part of
	the AEROLITH study.
	• Adverse Events by type, over time, severity, seriousness, and relatedness. AEs will be
	tabulated and summarized as counts and percentages. AEs will also be cross
	tabulated according to:
	- Severity
	- Unanticipated Adverse Device Effect (UADE)
	 Seriousness (Serious Adverse Event (SAE), Non-serious AE) Device Relatedness (Uprelated Ressibly Related Probably Related
	 Device-Relatedness (Unrelated, Possibly Related, Probably Related, Definitely Related)
	 Procedure-Relatedness (Unrelated, Possibly Related, Probably
	Related, Definitely Related)
Statistical Analyses	A sample size of 196 subjects randomized 1:1 to the investigational arm (Acoustic
/ Sample Size	Enhancer with URS-LL) and the control arm (URS-LL) was selected based on consideration
	of the primary endpoint. Assuming no more than 10% non-evaluable subjects, this

Justification:	provides a randomized sample size of 176 subjects (88 per arm).	
Justification.	The primary hypothesis test for the treatment success outcome is as follows:	
	The printing hypothesis test for the treatment success outcome is as follows.	
	H ₀ : $p_{AE} \le p_{Control}$ vs H ₁ : $p_{AE} > p_{Control}$	
	A one-sided p-value of 0.025 on a Farrington-Manning test will be used test will be used to indicate statistical significance. Assuming a response rate of 55% in the control arm and 75% in the investigational arm, the sample size of 88 per group provides 80% power for the primary hypothesis. Adjusted for a 10% drop-out, a total sample size of 196 was proposed.	
Study Success	The study is considered a success if the primary effectiveness endpoint is met with statistical significance and any safety findings are offset by the benefit in improved response when risks and benefits are weighed.	
	Statistical significance for the primary effectiveness endpoint is achieved when the one- sided p-value for the Farrington-Manning test when comparing the Treatment Success rates between the investigational arm (Acoustic Enhancer with URS-LL) and the control arm (URS-LL) is less than 0.025.	
	Statistical significance among any of the other effectiveness endpoints is not needed for Study Success.	
References:	CLIN-0001: Acoustic Enhancer Patient Informed Consent	
	CLIN-0002: Image Acquisition Protocol, Acoustic Enhancer Research in Laser Lithotripsy	
	CLIN-0003: Radiographic Evaluation Protocol of Applaud Medical's Acoustic Enhancer	
	with Laser Lithotripsy System in the Treatment of Urinary Stones	
	LBL-014: Acoustic Enhancer Instructions for Use	
	CLIN-0004: Acoustic Enhancer Clinical Study Investigator Agreement	
	CLIN-0005: Interim Clinical Report for Applaud Acoustic Enhancer with Ureteroscopic	
	Laser Lithotripsy	
	Laser Lithothpsy	

ABBREVIATIONS

AE ASA ASADE BMI CIP CT	Adverse Event American Society of Anesthesiologists Anticipated Serious Adverse Device Effect Body Mass Index Clinical Investigation Plan Computed Tomography
DMP	Data Management Plan
EC	Ethics Committee
eCRF	Electronic Case Report Form
IFU	Instructions for Use
IRB	Institutional Review Board
ISO	International Organization for Standardization
PCNL	Percutaneous Nephrolithotomy
SADE	Serious Adverse Device Effect
SAE	Serious Adverse Event
SWL	Shockwave Lithotripsy
TGA	Therapeutic Goods Administration
UADE	Unanticipated Adverse Device Effect
USADE	Unanticipated Serious Adverse Device Effect
URS	Ureteroscopy

	Name, Address and Contact		
Principal Investigator	TBD		
Study Sponsor Contact	[name]		
	Executive Vice President of Regulatory, Clinical, and		
	Quality Affairs		
	Applaud Medical, Inc.		
	[name]		
	[name]		
	[contact]		
	E-mail: [contact]		

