5.8. Exclusion Criteria

- 5.8.1. Patients with stones exceeding 20 mm in cumulative diameter on the side to be treated. *Note:* Punctate stones measuring ≤ 2mm do not count in the cumulative diameter limit.
- 5.8.2. Patients with ureteral stones located distal to the iliac vessels on the side to be treated
- 5.8.3. Diagnosis of radiolucent stones (on the side to be treated) on KUB or Scout CT Images
- 5.8.4. For patients who have a ureteral stent in place, patient is excluded if stent is calcified or encrusted as verified using standard of care imaging (e.g., KUBX-ray)
- 5.8.5. Patients who have had prior URS-LL within 3 months on the side to be treated at the time of consent
- 5.8.6. History of cystinuria
- 5.8.7. Urine pH is < 5.5. **Note:** If a patient's largest stone measures a mean stone intensity of ≥500 HU and the patient has a historical pH value of ≥ 5.5, a recently tested (within 30 days of consent) urine pH showing <5.5 in this case does not exclude a subject.
- 5.8.8. Patients with known history of recurrent uric acid stones.
- 5.8.9. Untreated urinary tract infection (UTI)
- 5.8.10. History of drug resistant chronic UTI
- 5.8.11. If female, pregnant as confirmed using urine or serum test to be conducted on the day of the procedure
- 5.8.12. Patient has an American Society of Anesthesiologists (ASA) physical classification level of 4 or greater.
- 5.8.13. Known sensitivity to possible medications used before, during, or after the URS laser lithotripsy procedure, including but not limited to the following: sedative agents, general anesthetics, topical anesthetics, and opioid analgesics
- 5.8.14. Stones suspected in calyceal diverticula
- 5.8.15. Horseshoe kidney
- 5.8.16. Congenital ectopic pelvic kidneys
- 5.8.17. Full staghorn calculi >2cm
- 5.8.18. Patients with elevated serum creatinine > 1.5mg/dl
- 5.8.19. Patients with solitary kidney
- 5.8.20. Malrotated kidney on the side with urinary stone
- 5.8.21. Duplicated collecting system or duplicated ureters
- 5.8.22. Patients who are currently involved in any investigational drug or device trial or have been enrolled in such trials within 30 days of index procedure
- 5.8.23. Patients who are actively taking antiplatelet and anti-coagulation except low dose aspirin
- 5.8.24. Prostate biopsy within the last 3 months
- 5.8.25. History of radiation therapy of abdomen and pelvis

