7.3. Randomization Assignment: Acoustic Enhancer with Ureteroscopic Laser Lithotripsy (Investigational Arm) vs. Standard Ureteroscopic Laser Lithotripsy (Control Arm)

Following consent and if a subject meets the study's inclusion/exclusion criteria, the subject will be randomly assigned to the investigational or control arm on the day of the procedure. If the potential subject does not meet the study procedure eligibility criteria, he/she will NOT be randomly assigned to treatment or the control arm. Random assignment will be conducted using an allocation ratio of 1:1 with one subject randomized to the Investigational Arm for each subject randomized to the Control Arm. Random assignment will be conducted block design generated separately for each clinical site. Subjects will be blinded to treatment allocation through index procedure.

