7.4. Double Blinding

This study is a double blinded study in which:

- Study subjects will not be informed of their treatment allocation through the index procedure.
- In assessing stone fragmentation using a CT image as defined in the primary endpoint, an independent radiologist will conduct the assessment and will be blinded to the treatment allocation of each subject's CT image.

7.5. Point of Enrollment

After the patient signs the Informed Consent Form, all inclusion and exclusion criteria will be verified. If the potential subject meets all of the inclusion and none of the exclusion criteria, the potential subject will then become eligible for randomization. All subjects who sign the informed consent form will be entered in the Electronic Data Capture (EDC) system. Each site will assign a unique subject ID for each subject that signs an informed consent using three-digit site number and three-digit subject number. Each subject number will be assigned in consecutive order and will not be reused. Assigned subject numbers will be recorded on the Screening and Informed Consent Log (CAP-004-03). The Subject ID number will remain with the subject throughout the course of their involvement in the study. Those subjects who do not meet inclusion/exclusion criteria, withdraw consent prior enrollment, or were in the screening process while enrollment closed (also known as missed enrollment) will be appropriately documented in the EDC system.

Enrollment is defined as the time when the patient signs an IRB-approved informed consent form (thereafter becomes a study subject).

Potential subjects who fail to meet screening assessment requirements will be counted as a screen failure and will not be treated. Screen failure subjects will be exited from the study, and not evaluated for safety or effectiveness. Screen failures will be documented at the site on a screening log.

7.6. Subject Withdrawal or Discontinuation

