8. SUBJECT ASSESSMENT AND STUDY VISIT SCHEDULE AND PROCEDURES

8.1. Pre-Treatment Visit

After the subject has completed the informed consent process, research staff will review potential subject's medical history, including available images, to verify study subject's eligibility. In addition, research staff will conduct protocol required assessments prior to the index procedure to obtain baseline information and verify subject eligibility.

- As part of routine care, study subjects may be prescribed medications such as analgesics, alpha blockers, calcium channel blockers, antibiotics to take as needed.
- Research staff will review subject's medical history, including available images, to verify study eligibility.
- Subjects will complete a baseline health status and undergo focused urogenital calculus physical exam and vital signs.

- Subjects will undergo a CT scan to measure stone dimensions (in mm), and location (e.g., the upper (superior) pole, lower (inferior) pole, and interpolar region of the kidney, pelvis of the kidney, and proximal ureter). This will be noted on the Electronic Case Report Form (eCRF). If there are multiple stones, each one will need to be measured and its location (i.e., pelvis, ureter), size will be documented.
 - CT image acquisition parameters will follow CLIN-0002: Image Acquisition Protocol, AEROLITH Study. A CT image collected prior to screening may be used as baseline CT image. The CT image will be used to measure stone size and the location of the stone.
 - Measuring baseline stone size(s) will be conducted by the investigator following CLIN- 0003: Radiographic Evaluation Protocol of Applaud's Acoustic Enhancer with Laser Lithotripsy System in the Treatment of Urinary Stones
 - A Stone Size Measurement Verification Electronic Case Report Form (eCRF) will be completed by the investigational site and the baseline CT image will be uploaded to the core lab for analysis following CLIN-0003.
- Subjects will undergo a urinalysis to verify absence of Urinary Tract Infection (UTI) and verify pH level is ≥ 5.5. *Note:* If a patient's largest stone intensity is ≥ 500HU and has a historical pH value of ≥ 5.5, a recently tested (within 30 days of consent) urine pH showing <5.5 in this case is acceptable.
- Serum creatinine to verify renal function and serum creatinine is < 1.5mg/dl.

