The potential risks associated with the Acoustic Enhancer in the urinary tract during the investigational study procedure are:

Remote risks (≤ .01% of subjects)

 Acoustic Enhancer may cause an allergic reaction, which may range from minor itching or rash to major reaction such as anaphylactic reaction that could result in hospitalization or death. Excessive intraluminal pressure created by injection, causing backflow of urine and urinary tract rupture or urinoma formation

There is a potential risk associated with Acoustic Enhancer of an allergic reaction (less than 1 in a 10,000 subjects) or anaphylactic reaction (less than 1 in 20,000 subjects).

The placement of the Acoustic Enhancer closely resembles the manner in which irrigation fluid is delivered into the upper urinary tract in standard URS-LL. As such, there is a very low risk of adverse events associated with the increased pressures in the urinary tract arising during Acoustic Enhancer placement. Differential pressure risks include the pressure from backflow of urine in the urinary tract system, and in rare cases rupture in the urinary tract or urinoma formation.

As with any procedures in which ureteroscopes and other instruments are inserted into the urinary tract and materials placed using a cystoscope (narrow tube) into the urinary tract, in very rare cases, portions of the urinary tract could become inflamed or infected. While it is common practice to push a ureteral stone into the kidney prior to laser lithotripsy, there is also the potential risk of inadvertently doing so and of ureteral perforation from passage of the ureteroscope or other aspects of ureteroscope usage.

Significant new findings that may affect the subject's safety or willingness to continue in the study will be communicated to the study doctors and study subjects. An updated informed consent may be administered if appropriate.

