9.2. Potential Benefits

URS-LL is routinely performed to treat urinary stones. This use of Acoustic Enhancer in URS-LL has the potential benefit of reducing the residual fragment burden. Residual fragments following URS-LL are associated with post-operative morbidity, potential readmission, and longer-term sequelae, thus reducing residual fragments in URS-LL is increasingly prioritized in the endourology community. [8] [9].

Placing Acoustic Enhancer through the working channel of the ureteroscope prior to administration of laser energy and at additional intervals during the procedure also has the potential benefit of shortening the required lasering time, with associated benefits of reduced heat generation and shortened time under general anesthesia during URS-LL procedures.

CONFIDENTIAL Page 31 of 53

9.3. Mitigation of Risks

Risk to study subjects are mitigated in this study by the following:

- All investigations are conducted by investigators who are qualified by training and experience in the treatment of patients with urinary stones.
- All assessments are procedures performed in the controlled context of a clinical trial.
- Monitoring of the clinical trial to ensure compliance and with a focus on potential safety issues.
- All investigators will be trained to the Acoustic Enhancer IFU.

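### No eligibility criterion excludes known sensitivity to the Acoustic Enhancer or its components, although Protocol 9.1 lists allergic reaction, up to anaphylaxis and death, as a risk of the material

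*Protocol*

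**What the plan says.** Exclusion 13 in the Protocol Synopsis covers "Known sensitivity to possible medications used before, during, or after the URS" procedure, and the same criterion appears at 5.8.13. The examples that follow are sedatives, general anesthetics, topical anesthetics and opioid analgesics. The list is open-ended, but it is a list of medications.

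Protocol 9.1, under the risks of the Acoustic Enhancer material, says: "Acoustic Enhancer may cause an allergic reaction, which may range from minor itching or rash to major reaction such as anaphylactic reaction", and adds that such a reaction could lead to hospitalization or death. It classes the risk as remote and bounds it at fewer than 1 in 10,000 subjects for allergic reaction and fewer than 1 in 20,000 for anaphylaxis.

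Protocol 2.1 and 2.2 describe the material by class only: a perfluoroalkane gas core inside a lipid shell made from a phospholipid and two phospholipid-polymer materials.

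On process, Protocol 7.5 states: "After the patient signs the Informed Consent Form, all inclusion and exclusion criteria will be verified". Under 7.3, a subject who meets the criteria is then randomized on the day of the procedure. Of the four mitigation items in 9.3, the closest to this risk is "All investigators will be trained to the Acoustic Enhancer IFU".

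**The concern.** The protocol already treats known sensitivity as a reason to exclude, and it already names allergy as a risk of the device material. The two are not connected. The sensitivity screen covers drugs that both arms may receive and leaves out the one material given only to the investigational arm.

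Read literally, a patient with a documented sensitivity to a component satisfies every specific criterion and can be randomized, with an even chance of exposure. Whether that patient is stopped depends on the individual investigator or on a separate document. With up to 18 sites in the protocol (27 in SAP section 2), that need not happen in the same way everywhere. What is at stake is the safety of a very small number of patients. Operating characteristics are not in question.

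**Working it through.** The protocol states no figure on this point that could be reproduced. The check is a reading of the text, with a short calculation for scale.

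**Where a screen could be**

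| Place | Items | Items that screen for sensitivity to the device or a component |
|---|---|---|
| Protocol 5.7.1 to 5.7.7 (inclusion) | 7 | 0 |
| Protocol 5.8.1 to 5.8.27 (exclusion) | 27 | 0 |
| Protocol 8.1 and 8.2 (pre-treatment and day-of-procedure checks) | – | 0 |
| Protocol 9.3 (risk mitigation) | 4 | 0 |

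So none of the 7 + 27 = 34 criteria does so, and none of the four mitigation items.

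**Could an existing criterion cover it?**

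- *5.8.13.* Its scope is medications. Protocol 1.2 describes the Acoustic Enhancer as a single-use device, so the natural reading leaves it out.
- *5.8.27.* This lets the investigator exclude for other factors thought to interfere with taking part in or completing the study. Its examples concern consent, cooperation, follow-up and vulnerability; allergy is not among them. It permits exclusion but does not require it.
- *History review in 8.1.* Staff review "medical history, including available images, to verify study eligibility". The review is done against the criteria, and the criteria do not list this item.

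**Scale**

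Inputs: n = 98 in the investigational arm (Protocol 5.5); upper bounds p = 1/10,000 (allergic) and p = 1/20,000 (anaphylactic) from 9.1. Expected events = n × p; chance of at least one = 1 − (1 − p)^n.

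- Allergic: 98/10,000 = 0.0098; 1 − (1 − 0.0001)^98 = 0.0098, or about 0.98%.
- Anaphylactic: 98/20,000 = 0.0049; 1 − (1 − 0.00005)^98 = 0.0049, or about 0.49%.

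These are ceilings for unselected subjects. They do not measure how many events the added clause would prevent, because the documents give neither the number of candidates with a known component sensitivity nor a reaction rate for them.

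**Support for the bounds**

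Section 9.1 cites no source for them. The clinical experience described in section 4 is 27 treated subjects with no device-related event. Zero in 27 gives a one-sided 95% upper limit of 1 − 0.05^(1/27) = 0.105, about 10.5%. Those data alone cannot support a bound of 1 in 10,000.

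**The case against.** The strongest reply is that device contraindications normally sit in the IFU. Protocol 2.3 requires the product to be used according to the IFU, and the revision history says section 8.2 was aligned with an IFU revision approved by FDA. If that IFU contraindicates known hypersensitivity, one binding document already applies at every site. This stands as a limit on the finding: the IFU is not available here, so an overall lack of protection is not shown. What is shown is that the eligibility rules, against which subjects are verified before randomization, do not contain the exclusion or refer to the IFU for it.

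Other replies carry less weight.

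- Consent requires the risks to be explained, so a patient aware of a sensitivity might raise it. That helps, but it is not an eligibility rule.
- The SAP twice uses study-medication wording (sections 5.2 and 9.3), which might bring the product within 5.8.13. It may be template text, and the protocol consistently treats the product as a device.
- Almost nobody can have a known sensitivity to a new product. That is largely true of the product itself. It is less true of its components: Protocol 2.1 says perfluoroalkane gases are in routine use in retinal surgery, so earlier exposure to that class is possible.
- The risk is remote and few if any subjects would be affected. This is accepted, and it is why the point ranks low.

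**Conclusion.** The point holds as a low-cost safety improvement to consider. No criterion, pre-procedure check or listed mitigation screens for known sensitivity to the Acoustic Enhancer or its components, while the protocol itself names allergy up to anaphylaxis and death as a risk of the material. Few if any subjects would be affected, and the benefit of the clause cannot be quantified from the documents. There is no consequence for power, type I error or the primary analysis: under Protocol 7.6, a subject discontinued before general anesthesia is a screen failure and is outside every endpoint analysis.

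The conclusion rests on reading 5.8.13 as limited to medications and on the IFU content being unknown. An explicit IFU contraindication would reduce the change to copying it into the eligibility criteria.

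**What to change.** Extend exclusion 13 in the Synopsis and 5.8.13 with: *or to the Acoustic Enhancer or any of its components (e.g., lipid, phospholipid-polymer or perfluoroalkane components)*. Match the wording to any contraindication in the IFU. Give sites the actual component names, since the protocol names only classes and a site could not apply the criterion reliably without them. Check it at the existing medical-history review, before randomization, so that it applies equally to both arms.

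The cost is one clause in two places, one eligibility item on the case report form and a component list. No new assessment is needed, and the loss to recruitment should be negligible.
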